9.7.2 Primary Endpoint

The primary endpoint is the cumulative rate of any spontaneous abortion occurring on or before 12 weeks following oocyte retrieval in all subjects treated with PVR and undergoing fresh embryo transfer. Spontaneous abortion is defined as two positive β -hCG tests occurring at least two days apart on or after 2 weeks post-oocyte retrieval, but followed by observation of any empty intrauterine gestational sac (blighted ovum), intrauterine gestation without a fetal heart beat, or absence of viable fetuses, as documented by ultrasound.

In addition to the analysis specified in section 9.1, the number and rates of any spontaneous abortions (occurring on or before 12 weeks following oocyte retrieval) in all subjects in the mITT cohort will be analyzed as a sensitivity analysis using a Bayesian hierarchical model to dynamically borrow information from the DR-PGN-302 study. The cumulative rate of any spontaneous abortion from Study DR-PGN-302 was 55/549 (10.2%). Dynamic borrowing between this prior data and the current trial's data allow borrowing to occur to the extent indicated by these two observed rates. More borrowing occurs when the rates are similar while less when they differ. Full modeling details are provided in [Appendix 6](#).

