### 9.2 Primary Endpoint

The primary endpoint, spontaneous abortion, is defined as two positive  $\beta$ -hCG tests occurring at least two days apart on or after 2 weeks post-oocyte retrieval, but followed by observation of any empty intrauterine gestational sac (blighted ovum), intrauterine gestation without a fetal heartbeat, or absence of viable fetuses, as documented by transvaginal ultrasound (TVUS).

The derivation of this endpoint will be as follows:

- Any subject that has two positive  $\beta$ -hCG tests at least two days apart, and
- meeting at least one of the following conditions at visit 7P (4 weeks and 3-4 days post oocyte retrieval) or at a later visit:
  1. the TVUS assessment at a later visit shows that there is no presence of gestational sac,
  2. there is a presence of empty gestational sac,
  3. there is a gestational sac that has a fetus without a heartbeat, or
  4. any AE of pregnancy loss that meets the definition of spontaneous abortion.

In order to clearly identify AEs that are spontaneous abortions, listing of all AEs related to pregnancy loss, will be generated and provided to the medical team together with the reported and coded terms. [Appendix 3](#) lists the preferred terms associated with pregnancy loss that will be used for generating this listing. This listing will be provided periodically throughout the trial. The medical team will use these listings to identify AEs that meet the spontaneous abortion definition. The identification process will be completed prior to data base lock. Since spontaneous abortion can occur outside of scheduled visits, for accurate accounting of all spontaneous abortions, the AE eCRF page needs to be included.

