## Appendix 3 Preferred Terms Associated With Spontaneous Abortion and Ectopic pregnancy

All the preferred terms associated with Spontaneous abortion are listed below. This is based on MedDRA version 21.0. Prior to dry-run and DBL, the dictionary will be checked to make sure there is no change of terms with dictionary update.

Spontaneous abortion associated preferred terms
Abortion
Abortion complete
Abortion complete complicated
Abortion complicated
Abortion early
Abortion incomplete
Abortion incomplete complicated
Abortion induced
Abortion induced complete
Abortion induced complete complicated
Abortion induced complicated
Abortion induced incomplete
Abortion induced incomplete complicated
Abortion infected
Abortion late
Abortion missed
Abortion of ectopic pregnancy
Abortion spontaneous
Abortion spontaneous complete
Abortion spontaneous complete complicated
Abortion spontaneous complicated
Abortion spontaneous incomplete
Abortion spontaneous incomplete complicated

Abortion threatened

The relevant preferred terms associated with biochemical abortion are listed below. This is based on MedDRA version 21.0. Prior to dry-run and DBL, the dictionary will be checked to make sure there is no change of terms with dictionary update.

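### The scan conditions of the primary derivation ignore cause, so a selective reduction, or a termination followed by a non-required scan, would count as a spontaneous abortion

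*SAP*

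**What the plan says.** The primary objective (section 2.1 of both documents) is the rate of spontaneous recognised loss, blighted ovum included.

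The endpoint definition (Protocol 2.2, 7.1.2 and 9.7.2; SAP 2.2 and 9.2) asks for two positive β-hCG tests followed by an ultrasound finding. The last alternative, in Protocol 9.7.2, is "absence of viable fetuses, as documented by ultrasound".

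SAP 9.2 turns this into a rule. A woman with the two tests is an event on "meeting at least one of the following conditions at visit 7P" or afterwards. The four conditions are joined by an or:

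- Condition 1 is that "the TVUS assessment at a later visit shows that there is no presence of gestational sac".
- Condition 2 is the finding of a sac with nothing in it.
- Condition 3 reads "there is a gestational sac that has a fetus without a heartbeat", and so is again a finding on the scan.
- Condition 4 differs in kind, since it starts from the safety records: "any AE of pregnancy loss that meets the definition of spontaneous abortion".

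For condition 4, the medical team works through a listing of pregnancy-loss AEs before database lock. The listing is built from the preferred terms in SAP Appendix 3. Six of the terms under the spontaneous-abortion heading are for induced abortion, for example "Abortion induced complete".

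**The concern.** Conditions 1 to 3 describe what the scan shows, not how it came about. Only condition 4 refers to spontaneous abortion, and the definition it points to is the same scan-based one. The intended target is clear from the objective, but no operative rule enforces it.

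Two kinds of record are exposed:

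- **Selective reduction in a multiple pregnancy.** The woman remains pregnant and in the trial. A reduced fetus still visible in its sac at a later scan meets condition 3.
- **Elective termination of a viable pregnancy.** If any later scan is recorded, the empty uterus meets condition 1 and the closing words of the definition.

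Without a written rule, such a case would be settled ad hoc in an open-label, single-arm trial whose result is compared with a fixed 15%.

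**Working it through.** **Can the records arise?**

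- *Termination.* Women no longer pregnant are discontinued (Protocol 3.1.2). Ultrasound at Visit 9/early withdrawal and at Visit 10 is for women still pregnant (Protocol 6.3.8, 6.4). Footnote j of Table 6-1 says no scan is needed when early withdrawal is because the pregnancy has ended. The record therefore normally needs a non-required or unscheduled scan, which is not forbidden.
- *Selective reduction.* Up to two blastocysts may be transferred in some women (Protocol 7.3.10). A woman with a continuing pregnancy has the scheduled Visit 9 and 10 ultrasounds, which record sacs with and without heartbeat. No extra scan is needed. This assumes that condition 3 is read literally, as applying to any sac.

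**Is such a record removed elsewhere?** No. The described medical review covers the AE listing only. Protocol 8.3.7 names biochemical abortion, spontaneous abortion, ectopic and heterotopic pregnancy as losses to record as AEs, but not induced loss. Protocol 8.2.2 says procedures themselves are not AEs. An induced loss might therefore be missing from the listing while its scan still counts.

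**What does one event do?**

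Inputs: n = 240, two-sided exact 95% interval, threshold 15%, true rate 9% (SAP 3.3 and 9.3.1). The upper limit for x events is the 0.975 quantile of Beta(x+1, n−x).

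- x = 25: 14.99%, excludes 15%.
- x = 26: 15.47%, does not.

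The plan's own figure first. The chance of excluding 15% is P(X ≤ 25 | 240, 0.09) = 81.3%, against 81.8% simulated in SAP Table 2. The simulation standard error is √(0.813 × 0.187 / 10,000) = 0.4 points, so the figure reproduces.

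Now suppose k of the 240 women are miscounted and the other 240 − k have a true rate of 9%. The chance is P(X ≤ 25 − k | 240 − k, 0.09). The documents give no frequency; k = 0 to 2 is an assumption.

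| k | Expected observed rate | Chance of excluding 15% |
|---|---|---|
| 0 | 9.00% | 81.3% |
| 1 | (0.09 × 239 + 1)/240 = 9.38% | 75.6% |
| 2 | (0.09 × 238 + 2)/240 = 9.76% | 69.0% |

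At a true 8% the chances for k = 0, 1, 2 are 92.9%, 89.7% and 85.6%; at 10% they are 63.6%, 56.3% and 48.6%.

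**The case against.** The best case for leaving the text alone has five parts.

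- **Rarity.** These women are undergoing IVF, with at most two blastocysts transferred. Neither document mentions selective reduction, and the termination case needs a scan outside the schedule. This stands: the count may well be zero.
- **Direction.** A miscount raises the loss rate and makes 15% harder to exclude, which is conservative for a safety trial. Section 2 of both documents also declines to tie success to the primary outcome. This stands too, but the stated objective is to estimate the spontaneous rate, and an upward error is still an error.
- **Appendix 3.** A reader might infer that the induced-abortion terms are themselves counted as primary events. The documents do not support that. The terms only build a listing for medical judgement, and the same list includes threatened abortion. Their presence lets the reviewers see such cases.
- **Review of scan events.** SAP 9.2 does not say that scan-derived events bypass medical review. True, but it describes review only for AEs, and the definition the reviewers apply has no test of cause.
- **Risk of over-correction.** Excluding every termination with a heartbeat at its last scan could delete true losses. The scheduled scans at Weeks 6 and 10 are four weeks apart, so a pregnancy can fail in between and be evacuated without a new scan. This stands and shapes the fix.

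**Conclusion.** The gap is real but narrow. As written, SAP 9.2 and the matching protocol definition would classify a selective reduction seen at a scheduled scan, or a termination followed by a non-required scan, as a spontaneous abortion, contrary to the objective.

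Each such woman adds an event worth 1/240 = 0.42 points to the observed rate. The power losses in the table are conditional on one or two such women occurring, which is an assumption.

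Two stronger readings should be resisted. A reader might infer that terminations in general will be counted; the discontinuation and scan rules make that unlikely. A reader might also lower the cut-off by one or two events while keeping all 240 women at 9% risk, giving 74.9% and 67.5%; that treats the same woman both as a certain event and as still at risk. No sample-size or power figure in the plan is wrong on this point.

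**What to change.** Before database lock:

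- State in SAP 9.2 and Protocol 9.7.2 that a loss documented as elective termination or selective reduction of a viable pregnancy is not a spontaneous abortion under any of conditions 1 to 4 and is listed separately. The exclusion applies to that loss, not to the woman: a later spontaneous loss of a remaining fetus still counts.
- Keep the case as an event unless viability at the time of the procedure is documented. Evacuation of a non-viable pregnancy, or of one of unknown status, then still counts.
- Extend the medical team's pre-lock review to events derived from scans.
- Report the primary rate with and without the excluded cases as events, on the same mITT denominator. This also helps the Bayesian sensitivity analysis, because the documents do not say how induced losses were handled in the 55/549 that it borrows.

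The cost is two sentences in each document, a wider review and one more table line. Sites may need a query to confirm cause, particularly for a reduction, since the AE rules do not ensure that one is recorded. Moving the induced-abortion terms in Appendix 3 to their own block is optional.

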### 9.3 Primary Variable Analysis

The primary endpoint will be analysed for the mITT cohort.

#### 9.3.1 Analysis of the Primary Endpoint

The number and rate of any spontaneous abortions (occurring on or before 12 weeks following oocyte retrieval) for subjects in the mITT cohort will be summarized and the associated two-sided exact 95% confidence interval will be generated. Upon generating the two-sided exact 95% confidence interval, the upper bound of the interval will be assessed for whether it excludes or fails to exclude a spontaneous abortion rate of 15%.

### 9.3.2 Hierarchical Modelling Details for the Sensitivity Analyses

Define  $n_1$  as the number of subjects in the current trial and  $Y_{1i}$  as the indicator of spontaneous abortion for the  $i^{\text{th}}$  subject in the current trial where  $Y_{1i} \sim \text{Bin}(n_1, \pi_1)$ . Let  $\pi_1$  be the true rate of spontaneous abortions in the current trial.

The previous trial (Study DR-PGN-302) reported a spontaneous rate of abortion of 55/549. This prior information about abortion rate is incorporated into the modelling framework through a hierarchical model. Dynamic borrowing between this trial's results and the current trial's data allows borrowing to occur to the extent indicated by these two data sources. More borrowing occurs when the two rates are similar while less borrowing occurs when they differ. This "dynamic" borrowing property is distinct from other approaches which use a fixed informative prior or apriori assume an amount of borrowing between these two data sources. Let  $Y_0 \sim \text{Bin}(n_0=549, \pi_0)$  where  $\pi_0$  is the true rate of spontaneous abortions from the previous trial.

The parameter is transformed to the logit scale for modelling purposes. Let  $\theta_1 = \log(\pi_1/(1-\pi_1))$  and  $\theta_0 = \log(\pi_0/(1-\pi_0))$ . The hierarchical model assumes that  $\theta_0$  and  $\theta_1$  have an across studies distribution:

$$\theta_1, \theta_0 \sim N(\mu, \tau^2)$$

The across trial mean  $\mu$  and variance  $\tau^2$  are unknown and hence have a prior distribution which is combined with the data to produce estimates of  $\mu$  and  $\tau^2$ :

$$\mu \sim N(-2.2, 2.25)$$

$$\tau^2 \sim \text{IG}(0.125, 0.005)$$

The mean parameter  $\mu$  assumes a relatively vague prior on the original scale and centered at 10%. The variance component  $\tau^2$  controls the degree of borrowing among studies. Small values of  $\tau^2$  result in a greater degree of borrowing while large values of  $\tau^2$  correspond to less borrowing. The parameter  $\tau^2$  is estimated using the data, so the observed between studies variation is a key component of the model behavior. The prior specification on  $\tau^2$  corresponds to an inverse-gamma distribution with mean 0.2 and weight 0.25.

At the end of this trial, the Bayesian hierarchical model specified above and the spontaneous abortion rate in the current trial together with the spontaneous abortion rate in the previous trial (i.e. 55 spontaneous abortion among 549 subjects) will be used to estimate the posterior distribution of the spontaneous abortion rates in the current trial. This posterior distribution will be used to generate a 95% credible interval for spontaneous abortion rate in the current trial. Since this posterior distribution is intractable, MCMC method via Openbugs in R (e.g., [R2OpenBUGS](#)) will be used to generate samples from the posterior distribution and these samples will be used to generate the 95% credible interval. Finally, whether or not the 95% credible interval lies entirely below 15% will be assessed.

## 9.4 Secondary Endpoints

### 9.4.1 Spontaneous Abortion within 6 and 10 Weeks of Oocyte Retrieval

The frequency and proportion of subjects that have any spontaneous abortion during the trial within 6 and 10 weeks (i.e., up to 42 and 70 days) post-oocyte retrieval will be derived for subjects in the mITT and safety cohorts for subjects that had oocyte(s) retrieved. Associated 95% confidence intervals will also be presented.

### 9.4.2 Biochemical Abortions within 6 and 10 Weeks of Oocyte Retrieval

Biochemical abortion is defined as a positive  $\beta$ -hCG test (at 2 weeks and 2 weeks + 3-4 days post-oocyte retrieval) but followed by no observed gestational sac on a later TVUS, or followed by a negative  $\beta$ -hCG test. Additionally, a biochemical abortion can be defined by an AE that meets the definition of biochemical abortion (see [Appendix 3](#)). To allow for assessment that might occur outside the visit window, a subject will be considered to be biochemically pregnant if there are two positive assessments at least two days apart on or after 2 weeks post-oocyte retrieval.

The frequency and proportion of subjects that have biochemical abortion within 6 and 10 weeks (i.e., up to 42 and 70 days) post-oocyte retrieval will be derived for subjects in the mITT and safety cohorts for subjects that had oocyte(s) retrieved. Associated 95% confidence intervals will also be presented.

### 9.4.3 Ectopic and Heterotopic Pregnancies

At time of TVUS examination, ectopic and heterotopic pregnancies may be detected and recorded in the TVUS eCRF. These events may also occur outside such assessment visits and may be recorded in the AE CRF. The preferred terms associated with ectopic pregnancy are presented in [Appendix 3](#) and will be used to select and check for such terms. The frequency and proportion of subjects with ectopic and heterotopic pregnancies will be pooled from the two sources and summarized.

### 9.4.4 Positive $\beta$ -hCG

Positive  $\beta$ -hCG is defined as a positive serum  $\beta$ -hCG test at 2 weeks and 2 weeks + 3-4 days post-oocyte retrieval. To allow for assessment that might occur outside the visit window, a subject will be considered to be biochemically pregnant if there are two positive assessment at least two days apart on or after 2 weeks post-oocyte retrieval. The positive  $\beta$ -hCG rate will be derived for subjects in the mITT and safety cohorts for subjects that had oocyte(s) retrieved. Associated 95% confidence intervals for these event rate estimates will also be presented.

Subjects who do not have two  $\beta$ -hCG tests due to missing data, early withdrawal, or any other reason will be counted as not having positive  $\beta$ -hCG unless a positive result is observed at a later pregnancy assessment. For example, if the outcome of these  $\beta$ -hCG tests is missing and a TVUS confirms clinical pregnancy at a later date then  $\beta$ -hCG will be imputed as 'positive'.

#### **9.4.5 Clinical Pregnancy**

Clinical pregnancy is defined as a TVUS showing at least 1 intrauterine gestational sac with fetal heartbeat at 6 and 10 weeks (i.e., up to 42 and 70 days) post-oocyte retrieval. The frequency and proportion of subjects that are clinically pregnant at 6 and 10 weeks post-oocyte retrieval will be derived for subjects in the mITT and safety cohorts for subjects that had oocyte(s) retrieved. Associated 95% confidence intervals for these event rate estimates will also be presented.

For the clinical pregnancy rate derivation at 6 weeks post-oocyte retrieval, if a subject has missing TVUS assessment and no other TVUS assessment at a later date, the subject will be counted as not having a clinical pregnancy. In contrast, if there is a later assessment with at least 1 intrauterine gestational sac with fetal heartbeat, the subject will be imputed as having a clinical pregnancy at 6 weeks post-oocyte retrieval.

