6.3.7 Visit 8: Week 8 of Pregnancy (6 Weeks After Oocyte Retrieval)

Subjects will attend Visit 8, 6 weeks (42±2 days) after oocyte retrieval.

The following must take place at the visit:

- Vital signs
- TVUS to determine the presence and number of gestational sacs with/without fetal heart beat
- Pelvic examination (documentation of presence and grade [intensity] of any pain, irritation, abrasions, or lesions on the cervix or vagina or vaginal adhesions).
If any lesions or abrasions are found on the cervix or vagina or vaginal adhesions are noted, another examination will be performed 2-4 days later.
- Recording of any vaginal bleeding noted in the subject's bleeding log since the previous visit
- Assessment of vaginal hemorrhage
- Removal of PVR6 and insertion of PVR7.
Insertion of PVR7 can be performed either at the trial site or at home.
- Review of PVR diary
- Assessment of drug accountability
- Recording of use of any concomitant medication
- Recording of AEs
- Dispensing of IMP: the next 3 PVRs (PVR8, PVR9, and PVR10) will be distributed.
will be distributed.
The subjects will remove and insert the PVRs at home. Subjects will be instructed to replace the PVR every 7 days.

6.3.8 Visit 9: Week 12 of Pregnancy (10 Weeks After Oocyte Retrieval) / Early-withdrawal Visit

Visit 9 will occur 10 weeks (70 ± 2 days) after oocyte retrieval. If a subject discontinues the trial prematurely an Early-withdrawal visit should be scheduled as soon as possible and within 1 week after last dose of the IMP.

The following procedures / assessments must take place at Visit 9 / the Early-withdrawal visit, irrespective of whether the subject discontinues the trial prematurely or continues:

- Vital signs
- Blood collection for assessment of:
 - Clinical chemistry and hematology parameters
 - Endocrine parameters (progesterone)
- Urinalysis
- Complete physical examination (including weight and BMI calculation)
- Pelvic examination (documentation of presence and grade [intensity] of any pain, irritation, abrasions, or lesions on the cervix or vagina or vaginal adhesions).
If any lesions or abrasions are found on the cervix or vagina or vaginal adhesions are noted, another examination will be performed 2-4 days later.
- TVUS or abdominal ultrasound (pregnant subjects only) to determine the number of gestational sacs with/without fetal heart beat and estimate gestational age
- Recording of any vaginal bleeding noted in the subject's bleeding log since the previous visit

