7.2.2 Clinical Pregnancy

Clinical pregnancy is defined as a TVUS showing at least 1 intrauterine gestational sac with fetal heart beat at 6 and 10 weeks post-oocyte retrieval (Visit 8 and Visit 9). For clinical pregnancies, the number of intrauterine sacs and fetal heart beats will be recorded.

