### **10.4 Other Safety Variables**

#### **10.4.1 Bleeding Log Assessment**

At the start of PVR, each subject will receive a bleeding log. For each incidence of sanitary napkin use for bleeding/spotting, subjects will be instructed to record the date, time of day, and the severity of the bleeding. For each subject, for each day: the grade (intensity) of bleeding associated with each sanitary napkin use will be summed. The sum of the daily grades (intensity) of bleeding will be averaged by visit window (see [Table 4](#)) where the visit window will cover the subject's Bleeding Log recording period (i.e., from the start of the PVR to the End-of-trial visit). Finally, this subject data will be summarized across all subjects for the safety cohort by visit window. The summary will include mean, median, standard deviation, minimum and maximum.

The analysis outlined above will be repeated removing the date of fresh transfer, periods associated with AEs reported as vaginal hemorrhage, the primary endpoint of spontaneous abortion and information collected after the cessation of the use of PVR. For vaginal hemorrhaging, spontaneous abortion and biochemical abortion, this will be achieved by removing bleeding log assessment collected starting from two days prior to the start of such an event up to two days after the end of such an event. Furthermore, for subjects with any negative  $\beta$ -hCG result, the bleeding log assessment will be summarized.

For subjects that discontinue from PVR early, the bleeding logs will be calculated normally (as per [Table 4](#)) until PVR is discontinued. Bleeding log entries after the visit preceding the Early Withdrawal Visit and bleeding log entries after PVR is withdrawn will be assigned to Visit 9. At the end of study visit and beyond, bleeding log entries will be assigned to Visit 10.

**Table 4** Visits numbers, nominal visit days from oocyte retrieval date and associated visit windows

Visit	Nominal visit date from date of oocyte retrieval (Day 1= date of oocyte retrieval)	Visit window (Day 1= date of oocyte retrieval)
Visit 3	Day 1	
Visit 4	Day 2	Start of IMP - Day 3
Visit 5	Day 5	Day 4 – Day 9
Visit 6	Day 14±1	Day 10 – Day 15
Visit 6P	Day 17±1	Day 16 – Day 19
Visit 7	Day 21±1	Day 20 – Day 26
Visit 7P	Day 31 ±1	Day 27 – Day 36
Visit 8	Day 42±1	Day 37 – Day 56
Visit 9	Day 70±1	Day 57 – Day 77
Visit 10	Day 84	Day 78 – Day 90

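### The SAP's Day 42 and Day 70 cut-offs fall short of the permitted Visit 8 and Visit 9 windows, which distorts the 10-week clinical pregnancy rate and shifts some losses to a later count

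*SAP*

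**What the plan says.** The protocol sets the visit windows. Section 6.3.7: "Subjects will attend Visit 8, 6 weeks (42±2 days) after oocyte retrieval". Section 6.3.8: "Visit 9 will occur 10 weeks (70 ± 2 days) after oocyte retrieval". Protocol 7.2.2 ties clinical pregnancy to the scans at those two visits and sets no day limit.

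The SAP turns the same time points into day limits. SAP 9.4.5 gives clinical pregnancy "at 6 and 10 weeks (i.e., up to 42 and 70 days) post-oocyte retrieval", but its next sentence speaks of "subjects that are clinically pregnant at 6 and 10 weeks post-oocyte retrieval", which is status wording. SAP 9.4.1 counts spontaneous abortions "within 6 and 10 weeks (i.e., up to 42 and 70 days) post-oocyte retrieval", and SAP 9.4.2 applies the same limits to biochemical abortion.

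Two rules bear on late assessments:
- SAP 9.4.5 imputes a 6-week pregnancy when that scan is missing and a later one shows a heartbeat. It has no such rule for 10 weeks.
- SAP 9.4.2 and 9.4.4 allow for β-hCG tests outside the visit window. No similar allowance covers the Visit 8 and Visit 9 scans.

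SAP section 12, which lists differences from the protocol, does not mention the day limits.

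**The concern.** A subject can attend Visit 8 or Visit 9 in full compliance with the protocol and still have her scan fall after the SAP's cut-off for the time point which that visit is meant to supply.

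For pregnancy, the rule can be programmed in two ways that give different 10-week rates from the same data. For losses, the date matters. Protocol 8.3.7 records pregnancy losses as adverse events, and Protocol 8.2.2 dates an event found by examination to the day of that examination. A loss first seen at an in-window Visit 8 on Day 43 is therefore dated after the 6-week limit. At 6 weeks the handling is also uneven: a heartbeat on a late scan can be brought back by imputation, while a loss first seen on the same day cannot.

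At stake is the accuracy of secondary descriptive rates in a single-arm trial that judges safety on the totality of the data.

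**Working it through.** **1. The plan's own design figure.** The largest count out of 240 whose two-sided exact 95% upper limit is below 15% is 25. At a true rate of 9%, P(X ≤ 25 | n = 240, p = 0.09) = 81.3%, against 81.8% from simulation in SAP Table 2. The figure reproduces, and nothing in it depends on the 42- or 70-day limits.

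**2. Permitted days past the cut-off**, in elapsed days after retrieval:

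| Visit | Protocol window | SAP limit | Permitted days past the limit |
|---|---|---|---|
| 8 | 40, 41, 42, 43, 44 | 42 | 43, 44: 2 of 5 |
| 9 | 68, 69, 70, 71, 72 | 70 | 71, 72: 2 of 5 |

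**3. The 10-week pregnancy rate, two readings.** The documents give neither pregnancy rates nor visit timing, so the rates below are assumptions, applied to N = 240.

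*(a) Status at the Visit 9 scan, with scans after Day 70 uncounted and those subjects treated as not pregnant.* Subjects missed = 240 × true 10-week rate × share of scans after Day 70.
- Low end: 240 × 0.35 × 0.10 = 8.4
- High end: 240 × 0.55 × 0.40 = 52.8
- For a true rate of 45%, the reported rate is 45 × (1 − 0.10) = 40.5% to 45 × (1 − 0.40) = 27.0%

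*(b) Any heartbeat seen up to Day 70.* Subjects overcounted = 240 × 6-week rate × share of these lost by Week 10.
- Low end: 240 × 0.40 × 0.02 = 1.9, or 0.8 points
- High end: 240 × 0.60 × 0.10 = 14.4, or 6.0 points

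**4. The 6-week spontaneous abortion count.** Events moved = 240 × true 6-week rate × share first seen at Visit 8 × share of those visits after Day 42. All three rates are assumed.
- Low end: 240 × 0.06 × 0.25 × 0.20 = 0.7
- High end: 240 × 0.08 × 0.50 × 0.40 = 3.8

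These events enter the 10-week count and the 12-week primary count. In the same way, a loss first seen at Visit 9 on Day 71-72 leaves the 10-week count and enters the 12-week count.

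**5. The 6-week pregnancy rate.** A heartbeat seen on Day 43-44 is a later assessment under SAP 9.4.5, so the subject is imputed as pregnant at 6 weeks. This rate is largely protected.

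**6. Table 4 (SAP 10.4.1).** Its column is headed "Nominal visit date from date of oocyte retrieval (Day 1= date of oocyte retrieval". Visit 4 at Day 2 follows that convention. Visit 5 at Day 5 and Visit 8 at Day 42 are instead elapsed days, since the protocol puts them 5 and 42 days after retrieval. For Visits 8 and 9 it also shows ±1 where the protocol has ±2. If its Day 1 convention were carried into section 9.4, 3 of 5 permitted days would miss the limit, including an exactly on-time visit.

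**The case against.** The strongest reply is that 42 and 70 days are simply the literal conversion of 6 and 10 weeks, and that the protocol's analysis sections also count losses within 6 and 10 weeks. Losses can be dated through adverse event records between visits. Moving the limit to Day 44 for every loss would label some losses after 6 weeks as 6-week losses. That stands, and it is why the fix leaves the day limits in place for losses not found at a visit scan.

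Several stronger inferences are tempting but unsupported:
- *Losses are dropped.* They are not. They move to the next cumulative count.
- *The 10-week rate has become an ever-pregnant rate.* The day limit permits that reading, but the status wording in SAP 9.4.5 and the visit-based definition in Protocol 7.2.2 point the other way. The text is ambiguous.
- *Both 10-week harms occur together.* They largely exclude each other. If any heartbeat up to Day 70 counts, a late Visit 9 scan costs little because the Visit 8 scan already counts. If status counts, losses between the scans are not counted as pregnancies.
- *40% or 60% of subjects are affected.* These are shares of permitted days (2 of 5, 3 of 5). The documents do not say how visits spread over the window, and the 60% also needs a day convention that the SAP states only for the bleeding log.
- *Table 4 makes it worse.* Its wide bins (Day 37-56 and Day 57-77) hold an in-window Visit 8 or 9 under either convention. Its numbering is a separate inconsistency.
- *The primary endpoint needs a longer limit.* SAP 9.3.1 gives 12 weeks without a day count, so there is no such cut to correct.

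For biochemical abortion no material effect is shown. Scheduled detection rests on β-hCG tests through Week 3 and the scan at 4 weeks + 3-4 days, well before Day 42.

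**Conclusion.** The mismatch is exact: 2 of 5 permitted days at each of Visits 8 and 9 lie past the SAP's limit, and no rule maps a Day 71-72 scan back to 10 weeks. The 10-week clinical pregnancy rate carries the main effect. It is understated on the status reading if any Visit 9 scans come late in the window, and overstated on the other reading if any pregnancies are lost between the scans. With the rates assumed above, the error is 8 to 53 subjects in one direction or 2 to 14 in the other, out of 240. The day count is firm. The subject counts are only as good as the assumed rates.

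The effect on the 6-week loss count is small (0.7 to 3.8 events on assumed rates) and one of timing only. The primary analysis, sample size and power do not change. The point should be repaired before database lock, but it does not threaten the trial's main conclusion.

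**What to change.** - **SAP 9.4.5:** define 6- and 10-week clinical pregnancy as status at the Visit 8 and Visit 9 scans, with the protocol windows of 42±2 and 70±2 elapsed days after retrieval. Add a missing-scan rule for 10 weeks.
- **SAP 9.4.1:** assign a loss first detected at an in-window Visit 8 or Visit 9 scan to that visit's time point. Keep the 42- and 70-day limits for losses dated otherwise through adverse event records.
- **Day convention:** state that these are elapsed days after retrieval. Separately, reconcile Table 4's day numbering and its ±1 with the protocol.
- **No change** to the 12-week primary limit, the sample size or the power statement.

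The cost is SAP wording and minor programming, with no new data. The one drawback is small: a few losses dated Day 43-44 or Day 71-72 would be reported as 6- or 10-week losses.
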